3.4.2 Disclosure of DOD Sponsorship and Access to Research Records

The informed consent form shall include a statement that discloses that the DOD is supporting the research and that representatives of the USAMRMC have the authority to review research

records of any study participant. Study candidates have a right to decline participation in research based on the source of the funding.

3.4.3 Inclusion Criteria

Study participants are required to meet the following inclusion criteria:

Table 3.4.3-1 Inclusion Criteria	
1.	Provide a signed informed consent form and authorization allowing the disclosure and use of protected health information.
2.	The designated primary study eye must have at least one well-demarcated area of atrophy as imaged by fundus autofluorescence with a minimum diameter of 300 microns and all lesions together must add to less than or equal to 12 mm ² (equivalent to no more than 5 disc areas in a least one eye) and a BCVA of 20 ETDRS letters (20/400 Snellen equivalent) or better.
3.	Two (2) pathogenic mutations confirmed present, in the ABCA4 gene. If only one ABCA4 allele contains a pathogenic mutation, the patient shall have a typical Stargardt phenotype, namely at least one eye must have flecks at the level of the retinal pigment epithelium typical for STGD.
4.	The primary study eye must have clear ocular media and adequate pupillary dilation to permit good quality FAF and sd-OCT imaging in the opinion of the investigator.
5.	Be able to cooperate in performing the examinations.
6.	Be willing to undergo ocular examinations once every 6 months for up to 24 months.
7.	Be at least six years old.
8.	Both eyes can be included if inclusion criteria are fulfilled for both eyes.

3.4.4 Exclusion Criteria

Study candidates shall be excluded if they meet any of the following exclusion criteria:

Table 3.4.4-1 Exclusion Criteria	
Exclusion Criteria	
1.	Ocular disease, such as choroidal neovascularization, glaucoma and diabetic retinopathy, in either eye that may confound assessment of the retina morphologically and functionally.
2.	Intraocular surgery in the primary study eye within 90 days prior to baseline visit.
3.	Current or previous participation in an interventional study to treat STGD such as gene therapy or stem cell therapy. Current participation in a drug trial or previous participation in a drug trial within six months before enrollment. The use of oral supplements of vitamins and minerals are permitted although the current use of Vitamin A supplementation shall be documented.
4.	The site Principal Investigator may declare any patient at their site ineligible to participate in the study for a sound medical reason prior to the patient's enrollment into the study.
5.	Any systemic disease with a limited survival prognosis (e.g. cancer, severe/unstable cardiovascular disease).
6.	Any condition that would interfere with the patient attending their regular follow-up visits every 6 months for up to 24 months, e.g. personality disorder, use of major tranquilizers such as Haldol or Phenothiazine, chronic alcoholism, Alzheimer's Disease or drug abuse.
7.	Evidence of significant uncontrolled concomitant diseases such as cardiovascular, neurological, pulmonary, renal, hepatic, endocrine or gastro-intestinal disorders.

3.5 Primary and Secondary Outcome Variables

The primary outcome variable for the ProgSTAR study is the yearly rate of progression of STGD as reflected by the growth of atrophic lesions measured by FAF imaging.

The secondary outcome variables are:

- Yearly rate of progression of STGD using spectral-domain optical coherence tomography (sd-OCT) to measure the rates of retinal thinning and the loss of photoreceptors.
- Yearly rate of loss of retinal sensitivity as measured by microperimetry
- Yearly change in best corrected visual acuity (BCVA) by using the Early Treatment Diabetic Retinopathy Study (ETDRS) protocol.
- Correlation of the presence and/or progression of morphological abnormalities in FAF and sd-OCT images with visual function as measured by microperimetry and BCVA.
- Exploratory analysis to examine factors associated with disease progression, such as participant's use of vitamin A supplementation and mutations in the *ABCA4* gene.

3.6 Measures to Minimize/Avoid Bias

Data from all sites will be sent, using a standardized, de-identified electronic clinical report form (eCRF), to a central data management center at the Dana Center for Preventive Ophthalmology, Wilmer Eye Institute, The Johns Hopkins University School of Medicine, except in the case of data from retinal imaging procedures and microperimetry, which will be sent to a central reading center at the Doheny Eye Institute, Keck School of Medicine, University of Southern California for further processing. Each center shall undertake standardized collection of all data. Ophthalmic outcome data from the microperimetry, sd-OCT and fundus autofluorescence assessments will be electronically submitted from the site to the appropriate reading center via secure data upload through the reading center internet website.

Once processed and analyzed by the appropriate reading center, all data will be transferred electronically from the reading center to the Dana Center system via a secure transfer process. Only coded identifiers will be used to identify participants.

3.6.1 Blinding

Not applicable.

3.6.2 Study Data

Table 3.6.2 Study Data					
ASSESSMENT/ PROCEDURE DATA COLLECTION POINTS	BASELINE Visit 1 DAY 0	VISIT 2 MONTH 6	VISIT 3 MONTH 12	VISIT 4 MONTH 18	VISIT 5 MONTH 24
Informed consent, medical history, genotype information, demographics	X				
Inclusion/Exclusion criteria assessed	X				
ETDRS BCVA Data	X	X	X	X	X
Ophthalmic fundus exam ¹ Data	X	X	X	X	X
Autofluorescence imaging Data	X	X	X	X	X
Microperimetry ² Data	X	X	X	X	X
sd-OCT Data	X	X	X	X	X
Changes in medical and ophthalmic history Data	X	X	X	X	X
Vitamin A supplementation Data	X	X	X	X	X
Full-field electroretinogram ³ Data	X				
Exit from study ⁴					X

¹: Ophthalmic examination includes slit lamp examination, cataract grading, and dilated fundus examination

²: In selected centers

³: Only if a full-field ERG was not performed within the past 5 years.

⁴: If qualified, patients may exit the study before Visit 5 to participate in an investigational treatment study for STGD

3.7 Schedule of Data Collection

Screening and baseline visits may be combined into one visit if the inclusion criteria are fulfilled and the exclusion criteria do not apply. Follow-up visits will be approximately 6, 12, 18, and 24 months after baseline visit. For these follow-up visits, a time window of \pm five (5) weeks around the calculated, expected date of the follow-up visit is acceptable for the data to be included for that time point.

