3.7.1.1. Screening/Baseline (Day 0)

The Screening/Baseline visit consists of the entering of data resulting from examinations and procedures performed as part of Standard of Care during the participant's scheduled follow-up ophthalmology visit:

1. An explanation of the study and providing a copy of the consent forms (if not mailed ahead of the visit) to the study candidate
2. Signing of the informed consent for the study
3. Completion of a medical and ophthalmic history
4. Recording and documentation of demographic information
5. Recording and documentation of vitamin A supplement use
6. Recording and documentation of genetic mutations in the *ABCA4* gene
7. Measurement of refraction and best-corrected visual acuity (BCVA) using the Early Treatment Diabetic Retinopathy Study (ETDRS) Testing Protocol [32]
8. Microperimetry
9. Ophthalmic examination
10. Spectral-domain optical coherence tomography
11. Fundus autofluorescence

The order of the examinations may be changed by the investigator and examinations may be performed on different days.

Description of Standard of Care examinations and procedures the investigators will utilize to obtain data that will be collected for this study include:

Refraction and best-corrected visual acuity (BCVA) according to the Early Treatment Diabetic Retinopathy Study protocol [32]:

Visual acuity is measured at a distance of one or four meters. A separate sequence of letters is used for each eye. Patients are encouraged to read each letter, and instructed to guess if unsure. The vision score is then calculated.

Fundus-Autofluorescence (FAF) and spectral-domain optical coherence tomography (sd-OCT):

Images of patient's eyes are recorded using sd-OCT, and scanning laser ophthalmoscopy (cSLO) in order to acquire fundus autofluorescence images. The computer driven cameras used in these techniques use a beam of light to take images.

Microperimetry:

Patients undergo an examination of the retinal central visual field using Microperimetry. During this procedure patients press a button when they see a little light spot on a screen of a special computer monitor. This technique uses a beam of light to take images and the test takes about 30 minutes.

Full-Field Electroretinogram (FF-ERG):

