3.7.1.2. Follow-up visits

The follow-up visits consist of the entry of data resulting from the following Standard of Care examinations and procedures obtained from the patients' regular follow-up visits:

1. Confirm that the participant wishes to continue in the study
2. Review and documentation of changes in medical and ophthalmic history
3. Documentation of vitamin A supplement use
4. Refraction and best-corrected visual acuity (BCVA) using the Early Treatment Diabetic Retinopathy Study (ETDRS) Testing Protocol [32]
5. Microperimetry
6. Ophthalmic examination
7. Spectral-domain optical coherence tomography
8. Fundus autofluorescence

The data from the visits will be utilized in the study even if the order of the examinations change from visit to visit or between the practices of the different investigators, and the examinations are performed on different days (as long as the time window is respected).

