7.2. Statistical Analyses

Estimating **the yearly growth in the area of the atrophic lesion** as measured by fundus auto-fluorescence:

First exploratory analysis looking at the baseline, six, and twelve months overall distribution of the outcome will be performed, outliers and inconsistent measures will be identified and reviewed. Let Y_{iv} represent the area (or a transformation to achieve normality; e.g. square

root) of the i^{th} individual at visit v for $v=0, 1, 2, 3, 4$ for the baseline, 6 months, 12 months, 18 months and 24 months visits, respectively. In order to determine the average rate of progression in the population, an appropriate approach will be to allow for each individual to have his/her own intercept and slope and to average them to achieve the overall rate of decline. This is accomplished with a random coefficients regression model of the form:

$$Y_{iv} = (\mu + a_i) + (\Delta + b_i)v + \gamma Z_{iv} + e_{iv}; \text{ where } a_i \sim N(0, \sigma_1^2), b_i \sim N(0, \sigma_2^2), \text{ cov}(a_i, b_i) = \sigma_{12} \text{ and } e_{iv} \sim N(0, \sigma^2).$$

The a_i and b_i are the random departures of the line for the i^{th} individual from the population line with intercept μ and slope Δ . The e_{iv} are the within individual departures from the line of the repeated measurements taken on the i^{th} individual at times 0, 6, 12, 18 and 24 months. Z_{iv} represents a vector of factors that could to be related to progression such as age and use of vitamin A supplementation.

The estimate of Δ and its standard error will provide the six month progression of the lesions. In addition, to explore whether progression may be different for different initial levels, we will carry out the analysis in strata of baseline severity.

A similar approach to will be used to examine progression overtime for the secondary outcomes: retinal thinning, loss of photoreceptors, loss of retinal sensitivity, and changes of BCVA.

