7.4. Data Set Descriptions

Study Population

Patients with STGD enrolled into the study shall have had previous genetic testing and a finding of at least 2 pathogenic mutations in the *ABCA4* gene. If only one *ABCA4* allele containing a pathogenic mutation is detected, a patient may be enrolled if they have a typical Stargardt phenotype, i.e. at least one eye must have flecks at the level of the retinal pigment epithelium typical of STGD.

Data Sets for Endpoint Analyses

The final data set will include all participant visits. Most of the participants will complete 5 visits. Participants lost to follow-up after the six month visit shall be included but will only partially contribute to the estimation of the progression rates.

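### PROGSTAR-02 does not say how examinations outside the ±5-week windows are handled, and its visit-index model cannot place them at their true date

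*Protocol*

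**What the plan says.** PROGSTAR-02 section 3.7 sets the schedule: "Follow-up visits will be approximately 6, 12, 18, and 24 months after baseline visit". It then says that a window of plus or minus five weeks "around the calculated, expected date of the follow-up visit is acceptable for the data to be included for that time point".

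Section 3.7.1.2 says follow-up data will be used even when the order of examinations changes and "the examinations are performed on different days (as long as the time window is respected"). For baseline, section 3.7.1.1 says "The order of the examinations may be changed by the investigator and examinations may be performed on different days", and gives no limit on how far apart they may be.

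Section 7.4 reads differently: "The final data set will include all participant visits".

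The section 7.2 model uses a visit index v running from 0 to 4, "for the baseline, 6 months, 12 months, 18 months and 24 months visits, respectively", and its slope "will provide the six month progression of the lesions". Section 7 of the SMART protocol repeats that model.

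The SAP specifies a linear mixed model in which each participant has their own intercept and time slope, and reports change per year. It has no visit index and no window rule, and does not say whether time is actual or nominal.

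No section says whether an examination outside every window is excluded, assigned to the nearest visit, or analysed at its own date.

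**The concern.** Two analysts could follow this text and build different data sets for the primary endpoint. One would read sections 3.7 and 3.7.1.2 as an inclusion rule and drop off-window examinations. The other would read section 7.4 literally and keep them. The second analyst would then find that the section 7.2 model takes such an examination only if it is forced onto a nominal visit.

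Off-window examinations are foreseeable, because the data come from patients' regular clinic visits. The target is a yearly rate, so an examination at week 35 is as valid as one at week 26, provided its date is used. Dropping it loses information, and could select participants if late attendance is related to progression. Keeping it under the wrong time label mis-times it. In-window examinations share the timing problem to a smaller degree: one that is five weeks early or late is treated as on time.

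The retrospective study already avoids this. PROGSTAR-01 section 7.2 accepts variable intervals and regresses on actual times.

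**Working it through.** **1. The plan's own figure.** The documents give no figure for the effect of the windows. The checkable design figure is N = 170 in section 7.1 (difference 0.2 mm²/year, SD 0.9, two-sided 5%, 80% power, Wilcoxon).
- n = (0.9 × (1.960 + 0.842) / 0.2)² = 158.9.
- Dividing by the Wilcoxon relative efficiency 3/π gives 167, within 3% of 170. Simulated signed-rank power at 170 is 0.808.

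The figure reproduces, so SD 0.9 is used below.

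**2. The windows.** With 26 weeks per half-year, ±5 weeks gives weeks 21–31, 47–57, 73–83 and 99–109. The gaps between them are 47 − 31 = 73 − 57 = 99 − 83 = 16 weeks. The interval from baseline to the first window is 21 weeks.

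**3. Mis-timing inside a window.** With an on-time baseline, the largest error for one participant is 5/52 = 9.6% at month 12 and 5/104 = 4.8% at month 24. Two examinations in the same follow-up window can be 10 weeks apart.

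**4. One participant who loses month 24.** The measurement-error variance of a fitted slope is σ²/Sxx.
- Visits at 0, 0.5, 1, 1.5 and 2 years: Sxx = 1 + 0.25 + 0 + 0.25 + 1 = 2.5.
- Visits at 0, 0.5, 1 and 1.5 years: Sxx = 0.5625 + 0.0625 + 0.0625 + 0.5625 = 1.25.

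That component doubles for that participant.

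**5. Variance components.**
- Slope SD 0.9 mm²/year: the section 7.1 SD, treated as between-participant variation.
- Residual SD: the reader-reliability interval in section 7.1 is (0.02, 0.22) mm² in 34 eyes. The SD of a difference is 0.10/1.96 × √34 = 0.297, or 0.297/√2 = 0.21 per reading.
- Less favourable cases, both assumed: residual SD doubled to 0.42, and slope SD 0.5 with residual SD 0.42.

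**6. From one slope to the mean slope.** With individually fitted slopes, the variance of the mean is approximately (slope variance + σ²/Sxx)/N. Suppose every participant lost month 24:
- All visits: 0.81 + 0.0441/2.5 = 0.8276.
- Month 24 lost: 0.81 + 0.0441/1.25 = 0.8453.
- The standard error rises by √(0.8453/0.8276) − 1 = 1.1%.

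The doubling shrinks to about 1% because between-participant variation dominates.

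**7. Dropping all out-of-window visits.** This compares the generalised least squares standard error of the mean slope, N = 170, for all visits at actual time against in-window visits only. Deviations from target are assumed independent and normal. The random-intercept SD is set at 2.5 with no intercept–slope correlation (both assumed). The documents give no visit-timing data, so a range is shown.

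| Timing SD (weeks) | Follow-up visits out of window | SE rise: slope SD 0.9, residual 0.21 | SE rise: 0.9, 0.42 | SE rise: 0.5, 0.42 |
|---|---|---|---|---|
| 3 | 10% | 0.2% | 0.6% | 1.3% |
| 5 | 32% | 1.5% | 3.3% | 6.3% |
| 8 | 53% | 6.2% | 10% | 16% |

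**The case against.** The strongest reply is that section 3.7 only labels data. On that reading the window decides which nominal time point an examination belongs to, every visit stays in the data set, and sections 3.7 and 7.4 agree. This reading is open. A reader might infer that PROGSTAR-02 uses in-window data only, orders the rest discarded, and so contradicts section 7.4 outright. No section says that. Section 3.7.1.2 leans towards exclusion, but its condition sits in a sentence about examination order and different days. What stands is that the handling is unstated and the sections need reconciling.

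Second, the SAP is the later document and already models time with a yearly rate, so the visit-index criticism applies to section 7.2 and SMART section 7, not to the SAP. That is right. The SAP's remaining gap is that actual or nominal time is not specified.

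Third, the loss of precision is small. This also stands. A reader might carry the doubling in step 4 over to the study result, but it concerns one participant's measurement-error component. The 9.6% and 4.8% are single-participant worst cases as well: early and late visits partly cancel in a mean, although systematic lateness would not.

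Fourth, section 7.5 allows incomplete visit sets under maximum likelihood, plans a complete-data sensitivity analysis and mentions multiple imputation. That helps with missed visits. But if the window defines a usable visit, the complete-data check would itself leave out late attenders. The documents give no evidence that lateness is related to progression, so selection remains a possibility without a size.

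Finally, the SMART text states no window. It shares ProgStar's visits and statistical standards and repeats the visit-index model, so the model point applies to it directly and the window point only by inheritance.

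**Conclusion.** The point holds as an unreconciled rule with a better method readily available. Sections 3.7 and 3.7.1.2 tie use of follow-up data to the windows, section 7.4 includes all visits, and the section 7.2 index can represent neither an off-window examination nor the true date of an in-window one. Following the text can therefore drop or mis-time valid examinations, though it does not require that they be dropped.

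If the window is applied as an inclusion rule, the standard error of the mean slope rises by about 0.2% to 6% with variances derived from the documents, and by up to 16% in the least favourable case examined. These figures rest on assumed timing SDs of 3 to 8 weeks, on independent timing deviations, and on reading SD 0.9 as between-participant slope variation. If part of that 0.9 is measurement error, the loss moves towards the less favourable columns. The effect on precision is modest. The stronger reason to act is that the primary analysis data set and its time scale should not be left to choice after the data are seen.

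**What to change.** - In PROGSTAR-02 sections 3.7, 3.7.1.2 and 7.4, state that the windows serve scheduling and by-visit summaries only, and that all follow-up examinations enter the longitudinal model whatever their date.
- In section 7.2 and SMART section 7, replace v with actual years from baseline to the examination date. The slope is then a yearly rate directly, as the objectives require.
- In the SAP, state that time is actual elapsed time.
- Use each modality's own examination date where it was captured, and otherwise the visit date.

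A limit on the interval between paired examinations for structure–function correlations, such as the five weeks in PROGSTAR-01 section 3.7, could be considered. It is a preference and not needed for this correction.

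The cost is small: no extra visits, and slightly more data handling. It may not be wording alone. Sections 3.7.2.3 and 9.1 require the date of the visit, and no available text shows that each modality's date was recorded separately, so this must be confirmed first.

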3.7.1.1. Screening/Baseline (Day 0)

The Screening/Baseline visit consists of the entering of data resulting from examinations and procedures performed as part of Standard of Care during the participant's scheduled follow-up ophthalmology visit:

1. An explanation of the study and providing a copy of the consent forms (if not mailed ahead of the visit) to the study candidate
2. Signing of the informed consent for the study
3. Completion of a medical and ophthalmic history
4. Recording and documentation of demographic information
5. Recording and documentation of vitamin A supplement use
6. Recording and documentation of genetic mutations in the *ABCA4* gene
7. Measurement of refraction and best-corrected visual acuity (BCVA) using the Early Treatment Diabetic Retinopathy Study (ETDRS) Testing Protocol [32]
8. Microperimetry
9. Ophthalmic examination
10. Spectral-domain optical coherence tomography
11. Fundus autofluorescence

The order of the examinations may be changed by the investigator and examinations may be performed on different days.

Description of Standard of Care examinations and procedures the investigators will utilize to obtain data that will be collected for this study include:

Refraction and best-corrected visual acuity (BCVA) according to the Early Treatment Diabetic Retinopathy Study protocol [32]:

Visual acuity is measured at a distance of one or four meters. A separate sequence of letters is used for each eye. Patients are encouraged to read each letter, and instructed to guess if unsure. The vision score is then calculated.

Fundus-Autofluorescence (FAF) and spectral-domain optical coherence tomography (sd-OCT):

Images of patient's eyes are recorded using sd-OCT, and scanning laser ophthalmoscopy (cSLO) in order to acquire fundus autofluorescence images. The computer driven cameras used in these techniques use a beam of light to take images.

Microperimetry:

Patients undergo an examination of the retinal central visual field using Microperimetry. During this procedure patients press a button when they see a little light spot on a screen of a special computer monitor. This technique uses a beam of light to take images and the test takes about 30 minutes.

Full-Field Electroretinogram (FF-ERG):

With pupils dilated, patients remain in a darkened room for at least 20 minutes. Then, electrodes are placed close to the cornea, through the use of special contact lenses, to record the electrical response of the retina to light stimuli in a manner similar to an electrocardiogram recording.

Full field ERGs are performed according to ISCEV standards [33]. A standard for four different types of response measured include:

1. Rod response in the dark adapted eye
2. Maximal/combined response in the dark adapted eye
3. Cone response
4. Response to flicker

If an acceptable ERG was performed within the last 5 years, the test result will be used for the study data evaluation by the site investigators. The ERG is not generally recommended to be repeated if a previous ERG of more than 5 years ago was documented as unrecordable (absent responses) at that time.

An ophthalmic examination to diagnose the typical clinical appearance of STGD will aid in confirming eligibility for the study.

In order to participate in the study, all patients must have documentation of two (2) pathogenic mutations confirmed in the *ABCA4* gene from previously completed genetic testing. If only one *ABCA4* allele contains a pathogenic mutation, the patient should have a typical Stargardt phenotype, namely at least one eye must have flecks at the level of the retinal pigment epithelium typical for STGD. The genetic testing will have been previously completed and outside the scope of this study.

Before any study-related data is collected, the participants will have all imaging procedures explained to them, as well as what information from their procedure will be included in the study. Study participants must sign and date all appropriate informed consent forms before any data for the study is collected.

